### 2. Study Procedures

Enrolled menthol smokers will complete four, 2-hr long counterbalanced smoking sessions that are preceded by

## Addiction and Behavior Related to Menthol Cigarette Substitutes

12 hours of overnight tobacco abstinence, biochemically verified by exhaled carbon monoxide ( $eCO \leq 10\text{ppm}$ ). Sessions will be separated by a standard 48-hour washout period. Participants will smoke one cigarette ad libitum and a puff topography device will discretely record smoking behavior throughout the session, including puff duration, number of puffs, puff volume, and time between puffs.  $eCO$ , and self-report measures of craving and withdrawal will be recorded immediately before and at several times after the smoking session. Self-report measures of abuse liability will also be completed during the sessions. During the preferred study product observational use period, participants will be provided a weeks' worth of a potential menthol substitute at no cost. Consistent with our previous switching studies, study products will be provided in a 1.2 to 1 ratio based on self-reported use at the time of screening. This slight over appropriation helps to ensure that participants have enough study product available so to not artificially limit use, while also not oversupplying and potentially artificially increasing use behind what would be usual. Participants will be instructed to completely switch and exclusively use the study product during the 1-week time period. During this period, participants will complete daily diary once a day. Following the one-week use period, participants will come to the lab following 12-hr nicotine abstinence confirmed by  $eCO$ . To simulate the effect that restricting menthol in cigarettes would have on increasing (or not) preference for other alternative menthol substitutes, participants will complete a 90-minute concurrent choice task with differential cost (effort) required to earn 2 puffs from their UBMC (10 clicks increasing to 7200) versus their preferred study product (always 10 clicks) from Phase 2. . This session will last approximately 3 hours.

### Recruitment Feasibility and Retention

**Recruitment:** We intend to recruit 135 current menthol cigarette smokers (and assume 20% attrition) over a 16-month period (4 months of study preparation, 16 months of recruitment, and 4 months of data cleaning/analysis and manuscript prep). Therefore, we need ~6 participants to be recruited and complete study procedures each month to achieve our goal; we are confident that our recruitment approaches will yield sufficient numbers given our successful history of recruitment for other tobacco-related research of similar design. Menthol cigarette smokers will be recruited from advertisements through a variety of media outlets and the internet, including Study Search, as well as community events. Participants from other studies who have agreed to be contacted regarding other study opportunities will also be contacted. Staff from those studies will prepare contact letters/emails and call participants on behalf of this study. Participants interested will be referred to this study for screening. Participants will access the screening questionnaire using a public survey link generated by REDCap. Based on our team's previous studies we conservatively assume a 20% attrition rate; thus, we will need to recruit 135 participants to have 80 complete the study. Menthol smokers will be screened over the telephone. Participants who meet the following eligibility criteria will be asked to take part in the study.

**Inclusion Criteria:** 1) a current menthol cigarette smoker (>90% menthol cigarette use;  $\geq 5$  cigarettes per day) for at least the past 6 months, 2) between 21-24 (young adult or 25-50 years old (aged 25+), 3) willing to provide informed consent and abstain from all tobacco and nicotine use for at least 12 hours prior to the five lab sessions, 4) willing to complete two weeks of daily dairies, 5) read and speak English, and 6) have access to a smart phone or email

**Exclusion Criteria:** 1) self-reported diagnosis of lung disease including asthma, cystic fibrosis, or chronic obstructive pulmonary disease, 2) history of cardiac event or distress within the past 3 months, 3) currently pregnant, planning to become pregnant, or breastfeeding (will be verified with urine pregnancy test), 4) use of other tobacco products (e.g., e-cig, cigar, etc.) >5 days in the past month, 5) current marijuana use >5 days per month, 6) any use of other illicit drugs during the last 30 days , 7) *currently engaging in a smoking cessation attempt, and 8) currently using one of the alternative menthol study products, and 9) do not reside in the same household as a participant*

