## Addiction and Behavior Related to Menthol Cigarette Substitutes

### Abstract

Recent changes in population patterns of tobacco use in youth and adults underscore the potential substitution of other menthol tobacco products for cigarettes in the face of a ban on menthol in cigarettes. The increased use of cigars and pipe tobacco in youth following the 2009 ban on flavored cigarettes is particularly important given that flavored filtered little cigars are often indistinguishable from cigarettes and flavored pipe tobacco can be used to make roll-your-own cigarettes. Mentholated pipe tobacco (for roll-your-own cigarettes, mRYO), menthol filtered little cigars (mFLC), and non-menthol cigarettes (nmC) appear to be plausible substitutes for menthol cigarettes. The goal of the current study is to examine the abuse liability and substitutability of these potential menthol cigarette substitutes using an in-laboratory and *ad libitum* outpatient mixed design. One hundred current menthol cigarette smokers (n=50 aged 18-24 years, n=50 aged 25+ years) will complete a three-phase study: in Phase 1, utilizing a randomized crossover design, participants will complete 4 smoking sessions, smoking a different product each session to examine each product's abuse liability, demand, and topography. Products will include participants' usual brand menthol cigarette (UBMC) as well as 3 commercially-available alternatives, including mFLC, an mRYO product, and non-mentholated cigarette (nmC). Participants will complete one-week of daily diaries after smoking session 1 in phase 1 to assess their usage of usual brand menthol cigarette (UBMC). In Phase 2, to assess uptake, changes in subjective effects, and use over time, participants will select their preferred study product from Phase 1 and instructed to completely substitute the product for their UBMC for one week. Participants will complete daily diaries during this period to more accurately assess substitution and perceived effects in real-time. In Phase 3, participants will complete a final in-lab visit to assess the substitutability of their preferred product from Phases 1 and 2, under simulated ban conditions using a progressive ratio task. In all phases, multiple domains of abuse liability will be assessed, including product administration (in-lab topography and daily self-report measures), product liking/craving and withdrawal suppression (in-lab and daily diary self-report). This study will be the first to estimate the substitutability of potential menthol cigarettes substitutes in adult smokers, which could impact the health benefit of a public health standard banning menthol in cigarettes. It will evaluate characteristics and perceptions (e.g., satisfaction, taste) of these products that may increase the likelihood of substitutability. Findings from this study will provide key information on the potential unintended consequences of a ban on menthol in cigarettes (i.e., the extent to which these substitutes would appeal to and be used by existing menthol cigarette smokers). They may also inform how FDA treats other non-cigarette tobacco products used as menthol cigarette substitutes in future proposed rulemaking, for example, extending the ban to menthol filtered little cigars or menthol pipe tobacco.

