**The goal of the proposed study is to examine the abuse liability and substitutability of plausible menthol cigarette alternatives.** Using an in-laboratory and *ad libitum* outpatient mixed design, current menthol cigarette smokers (N=135) will complete a three phase, 3-week study: in Phase 1, utilizing a randomized crossover design, participants will complete [4 smoking sessions], smoking a different product each session to examine each product's abuse liability, demand, and topography. Products will include participants' usual brand menthol cigarette (UBMC) as well as 3 commercially-available alternatives, including mFLC, mRYO product, [*and non-mentholated cigarette (nmC).*] Participants will complete one-week of daily diaries after smoking session 1 in phase 1 to assess their usage of usual brand menthol cigarette (UBMC). In Phase 2, to assess uptake, changes in subjective effects, and use over time, participants will [*select their preferred study product from Phase 1*] and be instructed to completely substitute the product for their UBMC for one week. Participants will complete daily diaries during this period to more accurately assess substitution and perceived effects in real-time. In Phase 3, participants will complete a final in-lab visit to assess the substitutability of [*their preferred product from Phases 1 and 2,*] under simulated ban conditions using a progressive ratio task. In all phases, multiple domains of abuse liability will be assessed, including product administration (in-lab topography and daily diary self-report measures), product liking/craving and withdrawal suppression (in-lab and daily diary self-report).

**Aim 1: To assess the abuse liability of menthol cigarette alternatives.** *H1a: Alternatives will [have similar use topography and significantly reduce nicotine craving/withdrawal similar to UBMC, but (H1b) UBMC will show significantly greater demand indices and liking/satisfaction compared to alternatives. H1c: Among alternatives, nmC will show the greatest demand and liking/satisfaction, followed by mFLC, and lastly mRYO.]*

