### C. Approach and Preliminary Studies

Our team brings combined expertise in all areas necessary for the successful implementation of a clinical/clinical laboratory study examining the substitutability of other combusted mentholated non-cigarette tobacco products for menthol cigarettes. Specifically, our team has strong expertise conducting survey and longitudinal cohort research examining the 1) the role of menthol in smoking initiation, dependence, and cessation, 2) the impact of a menthol ban on population health including the substitutability of non-menthol and menthol cigarettes, and 3) the use of flavored and non-cigarette tobacco products among youth, young adults, adults. We have also conducted five clinical/human laboratory studies examining the pharmacological, toxicological, and physiological effects of non-cigarette tobacco products including two ongoing studies examining the impact of flavors and sweeteners on waterpipe tobacco smoking (R03DA041928; R03DA041928-02S1). In each of these studies, we assessed the abuse liability, topography, nicotine delivery, toxicant exposure, and use behaviors of the non-cigarette tobacco product under investigation. All of these methods are very familiar to our team and we have experienced great success utilizing them. Our team has also conducted several short-term as well as long-term randomized trials assessing tobacco use behavior. Lastly, our team has significant experience to collect daily diary data to examine tobacco use and behavioral correlates among smokers. These studies have resulted in excellent retention (>80%) with high-rates of daily diary completion (80-88%).

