## D. Research Design and Methods

### 1. Design Overview

**Figure 2** depicts the sequence of the proposed study. Using an in-laboratory and *ad libitum* outpatient mixed design, 135 current menthol cigarette smokers will complete a three phase, 3-week study. Over the 3-week study time period, participants will attend 5

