## E. Statistical Methods

### 1. Power Analysis

Since our main goal is to evaluate the substitutability of menthol alternatives in the context of a menthol cigarette ban, statistical power is based on differences in abuse liability measures (Hypothesis 1a) and product substitution (Hypothesis 2c). Sample size estimates relied on means and standard deviations of data collected as part of a University of Vermont laboratory study examining the abuse liability of cigarettes containing different doses of nicotine. A sample size of 80 subjects has 81% power to detect decreases in product satisfaction of up to 50% compared to their usual brand (mean for UBMC 5.5, SD 1.3). In addition, a sample size of 80 participants has greater than 80% power to detect decreases of 68%–72% in the cigarette purchase task indices of maximum expenditure, maximum price and price sensitivity, similar to what we found in our laboratory study. This sample size also provides 81% power to estimate 80% use of the preferred alternate product more than half the time during Phase 2 with a 95% confidence interval of 66%–94%.

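### The recruitment figures contradict each other (135 recruits, 20% attrition, 80 completers), and the 81% power for satisfaction does not follow from its stated inputs

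*Combined protocol and SAP*

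**What the plan says.** The Recruitment Feasibility and Retention section (under D.2) opens with "We intend to recruit 135 current menthol cigarette smokers (and assume 20% attrition) over a 16-month period" and then gives the derivation: "we conservatively assume a 20% attrition rate; thus, we will need to recruit 135 participants to have 80 complete the study". On accrual it says "we need ~6 participants to be recruited and complete study procedures each month to achieve our goal".

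Other sections give different totals:

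- Abstract: "One hundred current menthol cigarette smokers (n=50 aged 18-24 years, n=50 aged 25+ years) will complete a three-phase study".
- A. Specific Aims: "current menthol cigarette smokers (N=135) will complete a three phase, 3-week study".
- D.1 Design Overview: "135 current menthol cigarette smokers will complete a three phase, 3-week study".
- E.1 Power Analysis uses 80: "A sample size of 80 subjects has 81% power to detect decreases in product satisfaction of up to 50% compared to their usual brand". It prints a usual-brand mean of 5.5 and SD of 1.3.

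Section C reports retention above 80% in the team's earlier daily-diary studies. Section E.2 specifies repeated-measures ANOVA with Tukey adjustment and alpha 0.05. In Phase 1 every participant smokes all four products.

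**The concern.** The recruitment sentence presents 135 as the consequence of 20% attrition and 80 completers, and it is not. A reader cannot tell whether the trial expects to lose 20% or 41% of its participants, or whether 80 or 108 people will be analysed. If 20% and 80 are intended, the target is 35 people too high. If 135 and 80 are intended, the expected loss is double the rate called conservative, and it conflicts with the retention cited in section C. Observed accrual and attrition cannot be judged against targets that disagree.

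The power sentence has a related fault. Halving a mean of 5.5 when the SD is 1.3 is a very large effect for a within-person comparison of 80 people, so a power of only 81% looks wrong on its face. The sentence therefore does not tell the reader what the design can detect.

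**Working it through.** **Recruitment.** Inputs from Recruitment Feasibility and Retention: 135 recruits, 20% attrition, 80 completers, 16 months.

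- Recruits needed: 80 / (1 − 0.20) = 100. The plan says 135.
- Completers expected: 135 × (1 − 0.20) = 108. The plan says 80.
- Implied loss: 1 − 80/135 = 40.7%. The plan says 20%.
- Excess over the derived need: 135 − 100 = 35.

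Other routes to 135 also fail. Inflating by multiplication gives 80 × 1.20 = 96, and two successive 20% losses give 80/0.64 = 125.

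**Accrual over 16 months**, against a stated figure of about 6 per month:

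| Count | Per month |
|---|---|
| 135 recruits | 8.4 |
| 108 completers | 6.75 |
| 100 recruits | 6.25 |
| 80 completers | 5.0 |

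The closest match is 100 recruits, with 108 completers a looser one. Neither 135 recruits nor 80 completers fits.

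**Satisfaction power.** Inputs from E.1: n = 80, usual-brand mean 5.5, SD 1.3. A 50% decrease is 0.50 × 5.5 = 2.75 points. Two-sided alpha 0.05 is assumed, since E.2 does not state sidedness. The documents give neither the within-person correlation ρ nor the SD for the alternatives. I first take SD 1.3 for both products and let ρ vary.

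- SD of the difference = 1.3 × √(2(1 − ρ)). Its largest possible value, at ρ = −1, is 2.6.
- Noncentrality = (2.75 / SD of the difference) × √80. This gives 9.46 at ρ = −1, 13.4 at ρ = 0 and 18.9 at ρ = 0.5.
- The Tukey critical value for four products, on the t scale, is 2.587 with 237 df and 2.625 with 79 df.
- Power therefore exceeds 99.99% even at ρ = −1. The stated 81% is not reproduced.

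Treating the data as two independent groups does not recover it either: power is above 99.99% with only 20 per group.

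*Could an unequal SD explain 81%?* At n = 80, 81% power needs a standardised within-person difference of 0.388 (Tukey, 237 df), 0.393 (Tukey, 79 df) or 0.321 (unadjusted).

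- SD of the difference needed: 2.75/0.388 = 7.1, 2.75/0.393 = 7.0, or 2.75/0.321 = 8.6.
- With usual-brand SD 1.3 and an SD of the difference of 7.0, the alternative's SD would be 7.0 − 1.3 = 5.7 at ρ = −1, 6.9 at ρ = 0 and 7.6 at ρ = 0.5.

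Even the smallest of these exceeds the usual-brand mean of 5.5.

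*What 81% power does correspond to* (illustration only: SD 1.3 for both products, Tukey for four products). Detectable drop = standardised difference × 1.3 × √(2(1 − ρ)). The standardised difference is 0.388 at n = 80 (df 237) and 0.333 at n = 108 (df 321).

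| ρ | 80 completers | 108 completers |
|---|---|---|
| 0 | 0.71 points (13%) | 0.61 points (11%) |
| 0.5 | 0.50 points (9%) | 0.43 points (8%) |
| 0.8 | 0.32 points (6%) | not computed |
| 0.9 | 0.23 points (4%) | not computed |

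**The case against.** The strongest reply is that no analysis is endangered. With 135 recruits the trial reaches 108 completers at 20% loss, and still 80 at 40.7% loss, so the 80 behind E.1 is met either way. True power for satisfaction is higher than printed. This stands: the errors concern the stated design, not its adequacy. It does not make the contradictory figures acceptable, since enrolment target, expected loss and analysed number are basic design facts.

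A second reply is that 'recruited' might mean consented. Eligibility checks at the visits (pregnancy, exhaled CO, breath alcohol) could then reduce 135 to 100 starters (a 25.9% loss, 1 − 100/135), with 20% attrition taking 100 to 80. That would fit the abstract and the monthly figure. However, no such earlier loss is stated anywhere, and the recruitment sentence applies the 20% directly to 135. It is a reason to ask for 'recruited' and 'attrition' to be defined, not a resolution.

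Some corroborating detail is weak. The abstract's 100 may be a superseded target, because its 18–24 age band also differs from the 21–24 in the inclusion criteria. Saying that participants will complete a study may simply mean they take part. The match of about 6 per month to 6.75 is loose. None of this affects the main contradiction, which lies within one sentence.

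On power, 'up to 50%' is loose wording, and the source study's other inputs are not printed. The bound on the alternative's SD deals with the 50% drop. For smaller drops, the plan does not say which one has 81% power.

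**Conclusion.** The concern holds. The recruitment chain is wrong as written: 20% attrition with 80 completers means 100 recruits, 20% with 135 means 108 completers, and 135 with 80 means 40.7% loss. This part is pure arithmetic on the printed figures. The documents do not show which figure is out of date. The abstract and the monthly rate suggest that 135 replaced 100 without the rest being updated, but that is inference.

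The 81% satisfaction power is also not reproducible. With SD 1.3 for both products, power at a 2.75-point drop exceeds 99.99% for every possible correlation, and an unequal SD would need to be at least about 5.7 to bring it down to 81%. This is the lesser problem, because the satisfaction endpoint is not underpowered. The detectable-drop ranges rest on assumed correlations and an assumed common SD.

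**What to change.** Define 'recruited' and 'attrition', then adopt one chain and use it in the abstract, Specific Aims, Design Overview, Recruitment Feasibility and Retention, and Power Analysis:

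- (a) 100 recruited, 20% attrition, 80 completers. Over 16 months: 6.25 recruits or 5.0 completers per month.
- (b) 135 recruited, 20% attrition, 108 completers: 8.4 or 6.75 per month.
- (c) 135 recruited, about 41% attrition, 80 completers, with the reason for the higher loss: 8.4 or 5.0 per month.

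State whether the monthly figure counts recruits or completers.

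Replace the satisfaction sentence in E.1 with the drop detectable at 81% power for the adopted number of completers. State the assumed within-person correlation, the SD for the alternatives and the Tukey adjustment. The ranges tabulated above illustrate the calculation and are not proposed protocol text. Under (b), the other n = 80 statements in E.1 must be recomputed too.

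While E.1 is open, also check the 66%–94% interval around 80%. By the usual normal approximation its half-width of 14 points implies 1.96² × 0.16 / 0.14² ≈ 31 people, whereas n = 80 gives about 71%–89%.

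The cost is protocol wording, with no added participants. Under (a) the recruitment target falls to 100; under (c) the stated attrition becomes less favourable. The satisfaction power statement becomes more favourable.

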## Addiction and Behavior Related to Menthol Cigarette Substitutes

currently active (have not completed all study visits) in the study. If a participant is ineligible for the study at the time of screening, the participant can be reassessed at a later time to determine if they are now eligible i.e. A participant meets all other eligibility criteria, but is not eligible because they are currently pregnant or breastfeeding. The participant can submit a new screener after they are no longer pregnant or breastfeeding and can be reassessed for eligibility. Reassessment for eligibility will vary based on previous ineligibility criteria and will be determined on a participant by participant basis.

Participants' eligibility will be determined over the phone or via REDCap's online screener. Those who are eligible and willing to participate will be invited to sign an informed consent and complete their baseline visit in a private participant room at the Ohio State University. All participants will be given adequate time to review the informed consent with a trained research staff to help answer any questions that may arise during the consent process. Additionally, a copy of the informed consent will be given to all participants. A pregnancy test will be completed at the initial visit as well as before starting all the in-lab visits to ensure that the participant is not pregnant.

**Retention:** All participants will receive \$50 per completed in-laboratory session, \$7 for parking (when applicable), \$50 bonus for completing all sessions (up to \$335), and up to \$30 for completing daily diaries over the two week ad-lib and observational use periods (\$30 for 12 more diaries completed, \$25 for 11 diaries completed, \$20 for 9-10 diaries completed, \$15 for 7-8 diaries completed and \$0 for 1-6 diaries completed) for a total up to \$365. Consistent with our previous studies, payments will be made using the Greenphire ClinCard to increase accountability and facilitate ease of payment. We will also facilitate study calls/visits by offering evening and weekend appointments as well as additional retention strategies (e.g., multiple sources of contact, reminder calls/texts/emails). Participants will receive reminder calls in addition to email or text reminders. Reminders will be sent by text or email based on a participant's preferred method of contact.

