### **1. Potential Risks and Protections Against Risk**

There are minimal risks associated with this protocol. The protocol requires menthol smokers 21 to 50 years of age and older to undergo 12 hours of tobacco/nicotine abstinence on six occasions and to attempt to substitute another combusted mentholated nicotine product for their current combusted mentholated nicotine product. Tobacco/nicotine abstinence can lead to withdrawal symptoms that include irritability, anxiety, restlessness, hunger, and difficulty sleeping. The effects can be uncomfortable but are not dangerous. Risks and side effects related to the cigarette products that are commercially available include:

- Nicotine addiction: Nicotine is a highly addictive chemical found in cigarettes, and toxic at certain doses. It negatively affects the brain, nervous system and heart, and excessive exposure can result in poisoning, particularly in young children and pets. It also causes blood vessels to contract, increasing your blood pressure and pulse rates.
- Chronic diseases including COPD, bronchitis, emphysema, coronary heart disease, stroke and cancer.
- Smoking can also cause infertility and peptic ulcer disease, as well as slow the healing of wounds. It's the leading cause of preventable illness and death in the U.S.

The risk associated with substituting one combustible menthol product for another is also low. It is very unlikely that there is any difference in the level of harm between the participants' usual brand and the study products; therefore, substitution is unlikely to increase participants' exposure to harmful constituents over their usual brand. We are also attempting to mitigate the risk of artificially increased use due to receiving product by only giving participants study products in a 1.2 to 1 ratio.

We will withdraw participants who become pregnant, begin to breastfeed or receive diagnosis for a cardiovascular disease during the course of the study.

The risk of undermining smoking cessation is also potential risk; however, we will only recruit smokers not currently engaged in a smoking cessation attempt, and we will provide all participants at the end of the study with a referral to the Ohio Tobacco Quit Line ([name]).

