### **1. Adverse events**

Adverse events will be assessed by study staff at each follow-up visit via participant self-report and managed immediately. All adverse events will be reported to the OSU IRB. We will monitor for risk of smoking by screening participants for general medical precautions (pregnancy, cardiovascular disease). Any adverse events, breaks of confidentiality, or any other data or safety issues that arise will be discussed immediately between study personnel and [name]. [name] will be responsible for completing an Adverse Events Form should an event occur. [name] will report Serious Adverse Events to the OSU IRB within 24 hours of having received notice of the event. [name] will gather any information needed to investigate the event and to determine subsequent action. Any subsequent action will be documented and reported to the OSU IRB and the Program Officer at NIH. Adverse event reports will be reviewed annually with the OSU IRB to ensure participant safety.

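### As worded, exclusion criterion 2 does not reach a stroke, or a new coronary diagnosis without an event or distress, in the 3 months before entry

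*Combined protocol and SAP*

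**What the plan says.** **Entry.** In section D.2 (Recruitment Feasibility and Retention, Exclusion Criteria), criterion 2 excludes a "history of cardiac event or distress within the past 3 months". Criterion 1 is framed differently: it excludes a "self-reported diagnosis of lung disease including asthma, cystic fibrosis, or chronic obstructive pulmonary disease", with no look-back window. Criterion 3 covers pregnancy and breastfeeding. No other inclusion or exclusion criterion concerns the heart or blood vessels. The protocol says "eligibility will be determined over the phone or via" the REDCap online screener, and that after a failed screen "the participant can be reassessed at a later time to determine if they are now eligible".

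**During the study.** Section G (Potential Risks and Protections Against Risk) states: "We will withdraw participants who become pregnant, begin to breastfeed or receive diagnosis for a cardiovascular disease during the course of the study". The Design Overview in D.1 gives the length: "135 current menthol cigarette smokers will complete a three phase, 3-week study".

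**Safety text.** Section H.1 (Adverse events) says: "We will monitor for risk of smoking by screening participants for general medical precautions (pregnancy, cardiovascular disease"). It gives no definition, look-back or entry rule. Section G says of nicotine: "It also causes blood vessels to contract, increasing your blood pressure and pulse rates". It also lists both coronary heart disease and stroke among the risks of smoking.

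**The concern.** Section G names three reasons for withdrawal: pregnancy, breastfeeding and a cardiovascular diagnosis. Criterion 3 matches the first two at entry. The third is matched only in part, because criterion 2 speaks of a cardiac event or distress and not of a diagnosis or of stroke.

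Someone who had a stroke last month, or was told last month of coronary disease found without symptoms, could therefore meet no listed exclusion. The same diagnosis in week 2 would end participation. What is at stake is a small, avoidable safety exposure: overnight abstinence followed by smoking sessions, soon after such a diagnosis. No analysis is at stake.

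**Working it through.** **Step 1. Set the rules side by side.** The plan gives no figure to reproduce, so the main check is of wording.

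| Situation | In the 3 months before entry | During the 3 weeks |
|---|---|---|
| Heart attack | Barred (cardiac event) | Withdrawn |
| New coronary diagnosis with symptoms | Probably barred (distress, undefined) | Withdrawn |
| New coronary diagnosis, no event or distress | Not barred by any listed criterion | Withdrawn |
| Stroke | Not barred by any listed criterion | Withdrawn, if stroke counts as cardiovascular disease |

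Rows 3 and 4 are the gap. Row 3 needs no assumption about what cardiovascular disease covers; row 4 does. Long-standing stable disease is left out: a 3-month window is a coherent choice and can explain admitting it.

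**Step 2. Does H.1 close the gap?** It says that participants are screened for cardiovascular disease but not that a positive answer bars entry. The criteria in D.2 decide who is invited, and none of them carries H.1 into effect beyond the cardiac event or distress.

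**Step 3. How many people?** The documents give no rate, so the annual rate r below is an assumption. It stands for stroke plus new coronary disease without a cardiac event. The recruitment figure of 135 is from D.1 and D.2.

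- Chance that a recruit had such a case in the last 3 months: p = r × 0.25
- Expected number: 135 × p
- Chance of at least one: 1 − (1 − p)^135
- Applicants needed to fill 135 places if they are excluded: 135 / (1 − p)

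| Assumed r per year | p | Expected among 135 | At least one | None | Applicants needed |
|---|---|---|---|---|---|
| 0.05% | 0.000125 | 0.02 | 1.7% | 98.3% | 135.02 |
| 0.2% | 0.0005 | 0.07 | 6.5% | 93.5% | 135.07 |
| 1% | 0.0025 | 0.34 | 28.7% | 71.3% | 135.34 |

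Zero is the most likely count at every rate.

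**Step 4. Compare the two windows.** If the rate is constant, 3 months before entry (13 weeks) hold 13 / 3 = 4.3 times as many new cases as the 3 study weeks. This compares lengths of time only and says nothing about harm.

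**The case against.** The strongest objection is that the screener cannot be seen. H.1 says cardiovascular disease is screened for, and the phone or REDCap questions may already ask about stroke and recent diagnoses. This stands. A reader might infer that people with a recent stroke will in fact be enrolled; the documents do not support that. They show only that the listed criteria, followed exactly, would not stop it.

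A second objection is that entry and withdrawal rules may properly differ. Criterion 2 looks back for acute cardiac instability, while the rule in section G responds to a change in health under study supervision. This also stands in part. A reader might infer that the two rules contradict each other, but they do not: both can be followed as written. The difference in purpose explains admitting old, stable disease. It does not explain admitting a diagnosis a few weeks old, inside a window that the protocol itself treats as relevant.

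Third, both cases are narrow. Distress is undefined and may catch some new coronary diagnoses, and no section defines cardiovascular disease. The coronary case is therefore limited to diagnoses made without an event or distress, in applicants aged 21 to 50.

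Finally, the consequence is slight. Participants already smoke at least 5 cigarettes a day, and section G judges a difference in harm between their usual brand and the study products very unlikely. That is correct, and it sets the weight of the point.

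**Conclusion.** The point holds as a matter of wording. By the listed criteria, a stroke, or a new coronary heart disease diagnosis without an event or distress, in the past 3 months does not bar entry. The withdrawal rule in section G and the screening statement in H.1 both suggest a wider concern than criterion 2 expresses.

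It rests on the criteria as written, with the screener unseen, and for the stroke case on counting stroke as cardiovascular disease. The rates are assumed, so the counts show scale only: 0.02 to 0.34 people expected among 135.

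It would be too strong to call this a demonstrated safety failure. The added risk is small, and no estimate, test or conclusion is affected. It is a cheap improvement for the sponsor to consider.

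**What to change.** Reword criterion 2 with a closed list: 'cardiac event, cardiac distress, stroke, or a new self-reported diagnosis of coronary heart disease, within the past 3 months'. Ask exactly this in the phone and REDCap screener, if it is not already asked.

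Do not write an open category such as cardiovascular disease with an example in brackets. That could exclude newly diagnosed hypertension, and the cost figures above do not cover it.

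The cost is one reworded criterion and one self-report item, in the diagnosis form that criterion 1 already uses. Very rarely an otherwise eligible applicant is deferred. At the assumed rates, fewer than one extra applicant is needed to fill 135 places, and D.2 allows reassessment later.

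The change does not remove every difference between the rules. Disease older than 3 months would still be admitted, and H.1 would still mention screening without a time limit. Whether to go further is the sponsor's choice.
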